2.4.4 Analyses of efficacy endpoints

The primary analysis population for the efficacy endpoints will be the randomized ITT population which includes all patients who have been allocated to a randomized treatment regardless of whether the treatment kit was used or not. The efficacy analyses will be conducted according to the treatment to which they were randomized.

2.4.4.1 Analysis of primary efficacy endpoint(s)

Co-primary efficacy variables

The co-primary efficacy variables are: change from baseline in NC and in NPS (change from baseline in NC, NPS and LMK for Japan) at Week 24 assessed for dupilumab 300 mg q2w (pooled A and B arms) versus placebo, respectively.

The following null hypothesis and alternative will be tested for pooled dupilumab arms against placebo:

- H0: No treatment difference between the dupilumab dose regimen and placebo.
- H1: There is a treatment difference between the dupilumab dose regimen and placebo

Primary statistical model (ITT analysis)

Each of the 2 co-primary efficacy endpoints (3 co-primary efficacy endpoints for Japan) will be analyzed using a hybrid method of the worst-observation carried forward (WOCF) and multiple imputation. Data collected after treatment discontinuation will be included in the analysis. With this approach, for patients who undergo surgery for NP or receive SCS for any reason, data collected postsurgery (actual date) or post SCS will be set to missing, and the worst postbaseline value on or before the time of surgery or SCS will be used to impute missing Week 24 value (for patients whose postbaseline values are all missing, the baseline will be used to impute). For patients who discontinue the treatment without being rescued by surgery or receiving SCS, a multiple imputation approach will be used to impute missing Week 24 value, and this multiple imputation will use all patients who have not been rescued by surgery or receiving SCS at Week 24. Each of the imputed complete data will be analyzed by fitting an ANCOVA model with the baseline value of the corresponding co-primary endpoint, treatment group, asthma/NERD status, prior surgery history, and regions as covariates. Statistical inference obtained from all imputed data will be combined using Rubin's rule. Descriptive statistics including number of patients, mean, standard error, and least squares (LS) means will be provided. In addition, difference in LS means and the corresponding 95% confidence intervals (CI) will be provided along with the p-values.

Imputation and analysis model will be built with the following sample SAS code:

1. 40 datasets with a monotone missing pattern will be obtained, induced by Markov Chain Monte Carlo (MCMC) method on patients who have not been rescued by surgery or receiving SCS at Week 24.

```
proc mi data=dat_etd seed=14280 nimpute=40 out=dat_mc;  
  mcmc impute=monotone;  
  var asthma surgery region treatment basenps chg4nps chg8nps  
  chg16nps chg24nps;  
run;
```

2. For each of the imputed dataset with monotone missing pattern in step 1, the remaining missing data will be imputed using the regression method for the monotone pattern with adjustment for covariates including treatment groups, region, asthma/NERD strata, surgery strata and baseline value of the response variable.

```
proc mi data=dat_mc nimpute=1 seed=14280 out=dat_mi;  
  by _imputation_;  
  class asthma surgery region treatment;  
  monotone method=reg;  
  var asthma surgery region treatment basenps chg4nps chg8nps chg16  
  nps chg24nps;  
run;
```

3. Each of the 40 imputed datasets will be merged with the one dataset imputed by WOCF approach, and then be analyzed using the main statistical model. These 40 imputed datasets will be saved.

```
%macro w1;  
  %do i=1%to 40;  
    data wocf&i.;  
    set wocf;  
    _imputation_=&i.;  
    run;  
  %end;  
  data wocf_all;  
  set %do j=1 %to 40; wocf&j. %end;;  
  run;  
%mend w1;  
  
%w1  
  
data dat_imp;  
  set dat_mi wocf_all;  
Run;  
  
proc sort data=dat_imp;  
  by _imputation_;  
run;  
  
proc glm data= dat_imp;  
  by _imputation_;  
  class region asthma surgery treatment;  
  model = chg24nps = basenps asthma surgery region treatment;  
  lsmeans treatment / stderr;  
  estimate 'Diff Dupilumab vs Placebo' treatment -1 1;  
  ods output LSMeans=implsmeans Estimates=implsmeandiff;  
run;
```

4. Applying Rubin's rule to combine analysis results (point estimates and standard errors) from 40 imputations using PROC MIANALYZE for the LS means and difference in LS means between dupilumab and placebo. Sample code:

```
proc sort data=implsMeans; by trt01pn _imputation_;run;

proc mianalyze data= implsmeans;
  by trt01pn;
  modeleffects lsmean;
  stderr stderr;
  ods output ParameterEstimates=lsmeans;
run;

proc mianalyze data=implsmeandiff;
  modeleffects estimate;
  stderr stderr;
  ods output ParameterEstimates=lsmeandiff;
run;
```

Sensitivity analysis

For all sensitivity approaches, for patients who undergo surgery for NP or receive SCS for any reason, data collected post surgery or post SCS will be set to missing

Mixed-effect model with repeated measures (MMRM) approach

The model will include change from baseline values up to week 24 as response variables, and factors (fixed effects) for treatment, stratification factor (co-morbid asthma/NERD, prior surgery, region), visit, treatment-by-visit interaction, NPS/NC baseline value and baseline-by-visit interaction. An unstructured correlation matrix will be used to model the within-patient errors. Parameters will be estimated using restricted maximum likelihood method with the Newton-Raphson algorithm. The DDFM=KR will be used to compute the denominator degrees of freedom in the F-test. Data collected after treatment discontinuation will be included in the analysis. Descriptive statistics including number of patients, mean, standard error and LS means will be provided. In addition, difference in LS means, the corresponding 95% CI and the p-value will be provided for comparison of dupilumab against placebo. No imputation will be performed for the MMRM model.

If MMRM model fails to achieve convergence due to complexity of model specification, we will add some procedures to handle this issue including: 1) using maximum likelihood estimation instead of restricted maximum likelihood method; 2) covariance structure selection to reduce the number of unknown parameters to be estimated, the path is UN→TOEPH→TOEP→AR(1).

Pattern mixture model with copy increment from placebo

Each of the 2 co-primary efficacy endpoints (3 co-primary efficacy endpoints for Japan) will be analyzed with imputed missing value at 24 weeks using pattern mixture model with copy

increment from placebo (12). This copy increment from placebo implies that when subjects discontinue treatment early, they continue to take advantage of their previous therapy, but they progress in the same way as subjects in the placebo group.

The imputed dataset will be analyzed by fitting an ANCOVA model same as the one in primary analysis. Descriptive statistics including number of patients, mean, standard error, and least squares (LS) means will be provided. In addition, difference in LS means and the corresponding 95% confidence intervals (CI) will be provided along with the p-values.

Tipping point analysis

Each of the 2 co-primary efficacy endpoints (3 co-primary efficacy endpoints for Japan) will be analyzed with imputed missing value at 24 weeks as follows.

- **Step 1.** Monotone missing pattern was induced by Markov Chain Monte Carlo (MCMC) method using PROC MI: for patients who have intermediate missing values, the intermediate missing values will be imputed assuming a multivariate normal distribution over observations from all visits. 40 datasets with a monotone missing pattern will be obtained using this method.
- **Step 2.** For each of the imputed dataset with monotone missing pattern obtained in Step 1, the remaining missing data will be imputed using the regression method for the monotone pattern with adjustment for covariates including response variable, treatment groups, asthma/NERD strata, prior surgery strata, region, and baseline value of the corresponding endpoint. All available data in the monotone missing pattern data will be used. One imputed dataset will be obtained for each of the imputed dataset at Step 1. So, 40 fully imputed datasets will be obtained altogether.
- **Step 3.** The imputed values in Dupilumab group are added by a positive amount d for each imputed data sets.
- **Step 4.** The imputed values in placebo group are subtracted by a positive amount p for each imputed data sets.
- **Step 5.** Change from baseline in endpoint will be analyzed using ANCOVA model same as the one in primary analysis. Then the SAS MIANALYZE procedure will be used to generate statistical inferences by combining results from the 40 analyses using Rubin's formula.

Step 3 to Step 5 will be repeated iteratively until the p-value for treatment effect of dupilumab compared to placebo estimated in Step 5 is >0.05 .

LS mean difference between dupilumab and placebo in change from baseline in co-primary endpoints at Week 24 and the corresponding p-values will be provided for each combination of shift parameters.

Additional analysis

An additional analysis will be conducted on the 2 co-primary efficacy endpoints (3 co-primary efficacy endpoints for Japan) which includes all data including data collected after SCS for any reason and treatment discontinuation but excludes post NP surgery data. For patients who undergo surgery for NP, data collected postsurgery will be set to missing (as a comparison, data collected postsurgery and post SCS for any reason are both set to missing in the primary approach), and the worst postbaseline value on or before the time of surgery will be used to impute missing Week 24 value (for patients whose postbaseline values are all missing, the baseline will be used to impute). For patients who discontinue the treatment without being rescued by NP surgery, a multiple imputation approach will be used to impute missing Week 24 value, and this multiple imputation will use all patients who have not been rescued by NP surgery at Week 24. And data collected after treatment discontinuation or after SCS for any reason will be included in the analysis. The data will be analyzed in the same ANCOVA model for the primary approach. Descriptive statistics including number of patients, mean, standard error, and least squares (LS) means will be provided. In addition, difference in LS means and the corresponding 95% confidence intervals (CI) will be provided along with the p-values.

Mixed-effect model with repeated measures (MMRM) approach for NC as binary response data

In the primary analysis, NC will be analyzed as the average of 28-day nasal congestion data. To assess the robustness of this approach with respect to the ordinal categorical data nature of nasal congestion score, a MMRM approach on NC as longitudinal binary response data which gives statistical inference in terms of rate difference will be performed based on methods proposed and evaluated by Fan (13). First, the data will be processed to a repeated measures binary data format to facilitate the use of methods for longitudinal binary response data as follows.

- a. Baseline: the baseline of the NC will be the median of the daily score in the 7 days prior to randomization if there are at least 4 observations during these 7 days; if there are less than 4 observations, the baseline of the NC will be the median of the last 4 daily scores prior to randomization. In both cases, if the median ends in a .5 score, round it up.

Justification: The primary analysis uses the mean. Assuming the NC symptoms are reasonably stable during these 7 days (observed in ACT12340), it deemed to be appropriate to use median here. Using median instead of mean is also in accordance with the ordinal categorical data nature of nasal congestion score.

- b. Week 24: for each day during study day 142 to study day 169, the change from baseline in scores will be re-coded as
 - i. =1 if a subject improves at least 1 category at that day.
 - ii. =0 if a subject does not improve at least 1 category at that day.

For a patient with observations during days 142 to 169 (28 days), he would have daily symptom improvement score as a 28-dimensional vector. Each element of the vector represents whether the subject shows improved symptom in nasal congestion on that day compared with baseline.

Missing data in any day during study day 142 to study day 169 will be imputed as not improved for that day (=0).

By such an approach, daily data are used in the model, and such data also preserve the categorical data nature of nasal congestion score. This approach gives statistical inference in terms of rate difference and has been theoretically and quantitatively validated (13).

In this model, factors (fixed effects) for treatment, stratification factors (region, co-morbid asthma/NERD and prior surgery), day, treatment-by-day interaction, baseline value as a categorical variable will be included. Generalized estimating equations (GEE) will be used to obtain statistical inference. A variance component working covariance matrix which is merely a weight matrix will be used in the model to obtain unweighted proportions. Descriptive statistics including number of patients, LS average proportion of patients with improvement across the 28 days, and corresponding standard error will be provided. In addition, difference in LS average proportion of patients with improvement, the corresponding 95% CI and the p-value will be provided for comparison of dupilumab against placebo.

Subgroup analyses

To assess the consistency in treatment effects across different subgroup levels, subgroup analyses will be conducted for the co-primary efficacy endpoints with respect to

- Age group (<65, ≥65 years)
- Gender (Male, Female)
- Region (Asia: Japan; Latin America: Argentina, Chile and Mexico; East Europe: Russia, Turkey; Western Countries: Australia, Belgium, Spain, Israel, Portugal, Sweden, Canada, USA)
- Territory (North America: Canada and USA; European Union: Belgium, Spain, Portugal, Sweden; Rest of World: Israel, Argentina, Australia, Chile, Japan, Mexico, Russia, Turkey)
- Race (Caucasian/White, Black/of African descent, Asian/Oriental, Others)
- Ethnicity (Hispanic or Latino, Not Hispanic or Latino)
- Baseline weight (<70, ≥70- < 90, ≥ 90 kg; <60, ≥ 60 kg)
- Baseline BMI (<25, ≥25- <30, ≥30 kg/m²)
- Prior NP surgery history (Yes, No)
- Asthma comorbidity (Yes, No)
- Asthma and/or NERD (Yes, No)
- NERD (Yes, No)
- Allergic rhinitis at baseline (Yes, No)
- SCS use during the past 2 years prior to V1 (Yes, No)

To assess the consistency of the treatment effects across the subgroup levels, subgroup analyses will be conducted for co-primary endpoints at Week 24. The analysis will be performed based on imputed datasets from the primary analysis.

To test the interaction between treatment and subgroup factor, an ANCOVA model incorporating subgroup-by-treatment interaction will be built for each subgroup factor. The model will include all the covariates in the main statistical model plus the subgroup variable (if not one of the covariates adjusted in the main model already) and the subgroup-by-treatment interaction. Statistical inference obtained from all imputed data will be combined using Rubin's rule. A p-value for the test of interaction will be provided based on the combined inference.

In each subgroup, the co-primary endpoints will be analyzed using the primary approach for co-primary endpoints, but on the specific subgroup of the imputed primary analysis population. Descriptive statistics including number of patients, mean, standard error, and least squares (LS) means for each subgroup will be provided. In addition, difference in LS means and the corresponding 95% confidence intervals (CI) will be provided for each subgroup.

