2.5.6 Pooling of centers for statistical analyses

Due to the large number of centers, the randomization is stratified by country. Due to small sample size in some countries, the countries will be pooled into regions as defined below for the analyses:

- Asia: Japan;
- Latin America: Argentina, Chile and Mexico;
- East Europe: Russia, Turkey,
- Western Countries: Australia, Belgium, Spain, Israel, Portugal, Sweden, Canada, USA.

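### The subgroup 95% intervals are combined without the residual degrees of freedom, so they are too narrow when a subgroup has fewer than about 20 to 30 patients and little is imputed

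*SAP*

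**What the plan says.** The primary model in SAP 2.4.4.1 imputes first ("40 datasets with a monotone missing pattern will be obtained, induced by Markov Chain Monte Carlo (MCMC) method"). It then fits an ANCOVA to each completed dataset, with baseline, "treatment group, asthma/NERD status, prior surgery history, and regions as covariates". SAP 2.5.6 says of region that "the countries will be pooled into regions as defined below for the analyses", and lists four regions.

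Step 4 combines the 40 fits by Rubin's "rule to combine analysis results (point estimates and standard errors) from 40 imputations using PROC MIANALYZE for the LS means" and their difference. One call handles the LS means; the other, "proc mianalyze data=implsmeandiff", handles the treatment difference. Each call names only the estimate and its standard error. Neither carries an EDF= option, and the error degrees of freedom from PROC GLM are not passed on.

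For subgroups the SAP states: "In each subgroup, the co-primary endpoints will be analyzed using the primary approach for co-primary endpoints, but on the specific subgroup", with LS mean differences and 95% intervals for each. The levels include "Race (Caucasian/White, Black/of African descent, Asian/Oriental, Others", as well as age 65 or over, NERD, and Asia, which is Japan alone. No separate combining rule is given for subgroups, and SAP 2.5.7 on statistical technical issues reads NA. No subgroup sizes are stated.

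**The concern.** When PROC MIANALYZE is not told the complete-data degrees of freedom, it is taken here to treat them as infinite and to use Rubin's large-sample value. That value reflects the number of imputations and the share of variance due to imputation, but not how many patients were fitted. For 360 patients this does not matter. For a subset of a dozen or so, the residual variance is estimated on very few degrees of freedom, and a near-normal critical value is too small.

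At stake is how the subgroup display is read. Intervals for the rarest groups would be labelled 95% while covering less, so an apparent effect or an apparent lack of one would look more certain than it is.

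**Working it through.** **The plan's own figures.** The plan gives no degrees of freedom or critical value for the combined inference, so there is no figure on this exact point to reproduce. The design power in SAP 1.3 does reproduce. After 25% dropout there are 180 and 90 patients, and sqrt(180 × 90/270) = 7.746. For NC, 0.534 × 7.746 − 1.960 = 2.18, giving 98.5%. For NPS, 0.588 × 7.746 − 1.960 = 2.59, giving 99.5%. The plan states 99% for each.

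**Degrees of freedom as coded.** With m = 40 and lambda the fraction of total variance due to imputation, df = (m − 1)/lambda² = 39/lambda².
- lambda 0.05: 15,600, critical value 1.960
- lambda 0.10: 3,900, critical value 1.961
- lambda 0.25: 624, critical value 1.964
- lambda 1 (the floor): 39, critical value 2.023

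Subgroup size does not enter.

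**Degrees of freedom available.** The full model has intercept 1 + baseline 1 + treatment 1 + asthma/NERD 1 + surgery 1 + region (4 − 1) = 8 parameters, leaving n − 8. A subset that fixes a covariate has fewer parameters. Japan alone loses the three region terms (n − 5). NERD = Yes loses the asthma/NERD term (n − 7).

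**Complete-data limit (lambda near 0, all eight parameters estimable).** Relative width is 1.960 divided by the t quantile; coverage is P(|t| < 1.960).

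| n | df | t quantile | relative width | coverage |
|---|---|---|---|---|
| 12 | 4 | 2.776 | 0.706 | 87.8% |
| 16 | 8 | 2.306 | 0.850 | 91.4% |
| 20 | 12 | 2.179 | 0.900 | 92.6% |
| 30 | 22 | 2.074 | 0.945 | 93.7% |
| 50 | 42 | 2.018 | 0.971 | 94.3% |
| 100 | 92 | 1.986 | 0.987 | 94.7% |
| 360 | 352 | 1.967 | 0.997 | 94.9% |

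For Japan alone (n − 5) the coverage would be 90.9% at n = 12 (df 7) and 93.1% at n = 20 (df 15).

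**Simulated coverage.** Imputation used a 360-patient model with m = 40, followed by ANCOVA in the subset. Each cell gives coverage as coded, then with EDF=.

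| n | 5% missing | 10% missing | 25% missing |
|---|---|---|---|
| 12 | 89.2 / 97.4 | 91.2 / 98.3 | 93.7 / 99.4 |
| 15 | 90.9 / 96.2 | 92.6 / 96.4 | 93.8 / 98.4 |
| 20 or 21* | 93.7 / 96.0 | 94.1 / 96.7 | 95.3 / 97.1 |
| 30 | 94.7 / 95.9 | 95.2 / 96.7 | 95.5 / 96.8 |

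*n = 20 in the 10% column, n = 21 in the others.

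A further simulation over 0 to 10% imputed gave 88–91% at n = 12, 92–93% at n = 16 and 92–94% at n = 20 as coded, and 95.5–98% with EDF=. The exact no-imputation limit at n = 16 is slightly lower, at 91.4%.

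**What EDF= does.** The Barnard–Rubin value is 1/(1/ν_m + 1/ν_obs), with ν_m = 39/lambda² and ν_obs = (edf + 1)/(edf + 3) × edf × (1 − lambda). At n = 20 and lambda 0.05, ν_obs = 13/15 × 12 × 0.95 = 9.88, so df is about 9.9 and the critical value is 2.23 instead of 1.96. For lambda 0.05 to 0.25 the critical value is 1.967–1.973 at n = 360, 2.09–2.13 at n = 30, 2.23–2.32 at n = 20 and 3.38–4.05 at n = 12.

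**The case against.** The code is labelled as a sample, so the final program might add EDF=, and Rubin's rule as named in the text does not exclude a small-sample adjustment. That is fair, but this is the only combining rule in the SAP, and nothing signals that subgroups will be handled differently.

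No small subgroup is documented. That stands: sizes of roughly 10 to 50 for the rare levels are an assumption.

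Heavier imputation offsets the shortfall: with 25% missing, coverage as coded is 93.7% at n = 12 and 95.3% at n = 21. That also stands. However, 25% is the planned dropout, not the imputed fraction. Rescued patients receive one carried-forward value, identical in all 40 datasets, and data after treatment discontinuation are kept, so lambda may well be low.

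The remedy is not uniformly closer to nominal. With 10% missing at n = 20, coverage is 94.1% without EDF= and 96.7% with it; at n = 30 it is 95.2% and 96.7%. This stands as a real downside, although the error becomes conservative.

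A reader might infer that the co-primary conclusion is at risk, or that 87.8% describes the small subgroups in general. The documents support neither. The whole-trial critical value moves only from 1.960 to 1.967. The 87.8% figure needs 12 patients, all eight parameters estimable and no imputation, and n − 8 is wrong for Japan alone.

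**Conclusion.** The point holds as a minor one about descriptive intervals. As coded, the subgroup critical value does not respond to subgroup size. For 0 to 10% imputed, coverage is about 88–91% at n = 12, 91–93% at n = 16 (exact limit and simulation taken together) and 92–94% at n = 20. From about n = 30 it is near nominal. These figures depend on assumed subgroup sizes and imputed fractions, and on the software default described above.

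The co-primary analysis is unaffected. Subgroup results lie outside the testing hierarchy in SAP 2.4.4.3, so no type I error claim changes. The formal consistency check is the interaction test, which comes from a separate model containing the subgroup-by-treatment term and not from the subset fits.

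**What to change.** In the subgroup analyses, output the actual PROC GLM error degrees of freedom from each subset fit and supply it through EDF= in the PROC MIANALYZE calls (the Barnard–Rubin adjustment). Use the fitted value, which is n minus the number of parameters estimable in that subset, and not a fixed n − 8; for Japan alone it is n − 5. One sentence in the subgroup section would settle this.

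The cost is one option in the code. Point estimates do not change. Small-subgroup intervals become wider and may be somewhat conservative: about 96–98% coverage at 12 to 20 patients with 0 to 10% imputed, and up to 99.4% at n = 12 with 25% missing. Adding the option to the main analysis and to the pooled FEV1 analysis (SAP 2.4.4.2.4) is optional and for consistency only. The effect on the main analysis is negligible, and the effect on FEV1 has not been quantified.

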#### ***11.4.2.4.4 Analysis of sub-groups with comorbid asthma/NERD and prior surgery***

For each subgroup factor, interaction tests will be carried out to investigate consistency of the dupilumab effect across different subgroups identified by that factor.

In addition, for these subgroups, comparisons at Week 24 will be analyzed between dupilumab 300mg q2w (pooled A and B arms) versus placebo, and comparisons at Week 52 will be analyzed separately between dupilumab 300mg q2w (Arm A) versus placebo, and between dupilumab 300mg q2w/q4w (Arm B) versus placebo. Details of these analyses will be provided in the statistical analysis plan.

In addition to the analysis in the current study, statistical analysis for subgroups with comorbid asthma and surgery will be further conducted using the pooled data of EFC14280 and EFC14146, and the details will be provided in the statistical analysis plan (SAP) for the Integrated Summary of Efficacy (ISE).

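### Subgroup interaction tests reuse primary-analysis imputations that contain no treatment-by-subgroup term, so they lean modestly toward finding consistency

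*SAP*

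**What the plan says.** SAP 2.4.4.1, Subgroup analyses, sets the data source: "The analysis will be performed based on imputed datasets from the primary analysis". On those data "an ANCOVA model incorporating subgroup-by-treatment interaction will be built for each subgroup factor", results are pooled by Rubin's rule, and "A p-value for the test of interaction will be provided based on the combined inference". The within-subgroup LS mean differences come from the same datasets, restricted to each level.

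The imputation is defined earlier in the same section. Rescued patients receive their own worst post-baseline value (WOCF), or baseline if there is none. Data collected after stopping treatment are kept. For the remaining missing values, "this multiple imputation will use all patients who have not been rescued by surgery or receiving SCS at Week 24". The regression step uses "adjustment for covariates including treatment groups, region, asthma/NERD strata, surgery strata and baseline value of the response variable". The sample code lists the variables as "var asthma surgery region treatment basenps chg4nps chg8nps", followed by the Week 16 and Week 24 changes. Neither text nor code has a product term.

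The SAP lists 14 subgroup factors. Only region, prior surgery and asthma/NERD are in the imputation model, as main effects. Asthma alone, NERD alone, age, gender, race, weight, BMI, allergic rhinitis, prior SCS use and the others are absent.

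Protocol 11.4.2.4.4 states the purpose: for asthma/NERD and prior surgery, "interaction tests will be carried out to investigate consistency of the dupilumab effect across different subgroups identified by that factor". Protocol 5.2 makes the effect in these subgroups a secondary objective, and Protocol 6.1 and 8.4 cap enrolment to support it.

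**The concern.** The analysis model estimates a term that the imputation model fixes at zero. An MI-filled Week 24 value carries a subgroup difference in treatment effect only as far as the patient's own earlier visits already show it. Two things follow. The estimated interaction shrinks toward zero in proportion to the MI-filled share. Rubin's formula does not recognise that the imputed values were drawn under a restriction, so its standard error exceeds the true sampling SD of the shrunken estimate.

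Both effects push the same way. The question is whether the effect is consistent, so a test that rejects too rarely favours the answer a reader would like to see. The separate subgroup estimates are drawn closer together for the same reason. At stake is the evidence on the asthma/NERD and prior-surgery subgroups, for which recruitment was deliberately shaped.

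**Working it through.** **1. The plan's own figure.** SAP 1.3 gives 240 versus 120 patients, 25% dropout (leaving 180 versus 90), two-sided alpha 0.05, and effect sizes 0.55/1.03 = 0.534 (NC) and 1.24/2.11 = 0.588 (NPS). Power is Φ(d/√(1/180 + 1/90) − 1.96), with √(1/180 + 1/90) = 0.1291.
- NC: 0.534/0.1291 = 4.14, power 98.5%.
- NPS: 0.588/0.1291 = 4.55, power 99.5%.
- Both: 0.985 × 0.995 = 98%.

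The stated 99%, 99% and 98% are reproduced. Neither document gives power for an interaction test.

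**2. Interaction test with no missing data.** Assume a 50:50 subgroup, in line with the cap of 180 out of 360. The cells are 120, 120, 60 and 60, and SE = 2.11 × √(2/120 + 2/60) = 0.472. For an interaction of 1.24, power is Φ(1.24/0.472 − 1.96) = 75%. For 0.62 it is 26%.

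**3. Dilution.** Let m be the MI-filled share and c the fraction of the interaction that observed earlier visits carry into the imputed value. The expected estimate is about 1 − m(1 − c) of the truth. With no interim visits c = 0, so the fraction is 1 − m: 0.95, 0.90, 0.85 and 0.75 at m = 5, 10, 15 and 25%.

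**4. Simulation.** Inputs from the plan: 240:120 patients, SD 2.11, main effect 1.24, 40 imputations, sequential regression MI, interaction ANCOVA, Rubin's rule. Assumptions not in the documents: interaction of 1.24 or 0, 50:50 subgroup, visit correlation 0.6, data missing completely at random, and effects at Weeks 4/8/16 equal to 60/75/90% of the Week 24 effect. There were 1000 runs per cell. The planned columns have the subgroup main effect in the imputation model. The last column adds its treatment interaction.

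| MI share | Interim visits | Estimate / truth, planned | Size, planned | Power, planned | Power, interaction imputed |
|---|---|---|---|---|---|
| 5% | yes | 0.98 | 0.037 | 0.70 | 0.73 |
| 10% | yes | 0.95 | 0.039 | 0.67 | 0.69 |
| 15% | yes | 0.91 | 0.030 | 0.64 | 0.69 |
| 25% | yes | 0.86 | 0.022 | 0.54 | 0.64 |
| 5% | no | 0.95 | 0.033 | 0.68 | 0.73 |
| 10% | no | 0.91 | 0.025 | 0.63 | 0.68 |
| 15% | no | 0.85 | 0.017 | 0.54 | 0.70 |
| 25% | no | 0.74 | 0.005 | 0.37 | 0.58 |

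The rows without interim visits match the formula in step 3. The 25% row with interim visits implies c = 1 − 0.14/0.25 = 0.44. With no true interaction and a 25% share, Rubin's SE is 0.515 against a true SD of 0.440 (interim visits), and 0.533 against 0.402 (none). With the term added to the imputation, the estimate is 0.97-1.02 of the truth and size is 0.037-0.065. If the subgroup factor is absent from the imputation model altogether, the ratios are similar (0.97 to 0.85 with interim visits).

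**5. Simulation error.** If the runs are independent, the SE of the power difference in the first row is √(0.704 × 0.296/1000 + 0.730 × 0.270/1000) = 2.0 points. The losses of 2-3 points should be read as small, not as exact. The 10-point loss at 25% is well outside noise.

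**6. Endpoints.** NPS and NC have interim values in the imputation. LMK has no post-baseline CT before Week 24 (Protocol 1.2; SAP Table 4), so its dilution follows the lower rows. The power figures are on the NPS scale. Only the ratios carry over to LMK.

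**The case against.** The strongest reply is that the MI-filled share should be well below 25%. Rescued patients are handled by WOCF and off-treatment data are kept. Under Protocol 10.3.1, patients stopping by Week 16 return for NPS at Week 24, and those stopping before Week 40 keep the symptom diary through Week 52. This largely stands, with one gap. Patients whose early-discontinuation visit falls after Week 16 and up to Week 40 are next asked back for NPS at Week 52. SAP Table 4 opens the Week 24 endoscopy window at Day 141, so a discontinuation visit on Days 114-140 counts as Week 16 and no Week 24 NPS is scheduled.

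It is also fair that these tests lie outside the testing hierarchy, that low power is their main limit even with complete data, and that Protocol 11.4.2.4.4 plans further asthma and surgery analyses on data pooled with the sister study. None of this removes the bias.

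Stronger readings are tempting but not supported:
- A reader might infer that every missing Week 24 value is generated under a uniform effect. WOCF values are the patient's own data, and interim visits carry part of any real interaction.
- A reader might infer a power loss of 20 points or more. That needs a 25% MI-filled share with no interim visits. The 25% in SAP 1.3 is a planning dropout rate with no timing attached, and it is not called the share filled by MI. The loss also assumes an interaction as large as the whole main effect.
- A reader might infer that the primary result is biased or that spurious interactions arise. The primary model has no interaction term, and the planned test rejects too rarely, not too often.

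**Conclusion.** The reuse of the datasets, the missing term and the direction of the bias are clear from the text. As planned, the interaction tests are conservative and the subgroup estimates are drawn together, but only through non-rescued patients filled by MI. The size cannot be fixed from the documents because they do not give that share. Under the assumptions in the working, the effect is slight at shares of 5-10% with interim visits. It is moderate at 25%: 14% shrinkage, power 0.54 versus 0.64, size about 2%. It is larger at 25% without interim visits: 0.74 of the truth, power 0.37 versus 0.58 on the NPS scale. A different correlation, interaction size or missing-data mechanism would change these figures. The point is worth correcting because it bears on a protocol secondary objective and the change is cheap, but it does not threaten the trial's main conclusions.

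**What to change.** In SAP 2.4.4.1, Subgroup analyses, replace the sentence on the data source.

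- At least for asthma/NERD, asthma, NERD and prior surgery, re-impute the non-rescued patients by the same two-step procedure, with the subgroup variable and its interaction with treatment in the imputation model. Imputing within treatment arm with the subgroup included is an equivalent route.
- Leave the WOCF values and the primary-analysis imputation unchanged. Use the new datasets for both the interaction test and the within-subgroup estimates.
- Report the interaction contrast with its 95% CI beside the p-value, and the MI-filled share by subgroup level and arm.
- For the remaining or sparse factors, collapse levels and re-impute, or keep the primary datasets and report that share so the reader can judge the dilution.

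The cost is SAP wording and extra MI runs per factor and endpoint. The four named factors are binary, so each adds one product term (plus a main effect for asthma alone and NERD alone). Intervals may widen slightly in small levels, and the subgroup datasets will no longer match the primary ones exactly, which a table footnote should say.
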